**AND**

- Experienced an investigator-determined confirmed radiographic disease progression after stopping their initial treatment with pembrolizumab (MK-3475)
- Did not receive any anti-cancer treatment since the last dose of pembrolizumab (MK-3475)
- Have a performance status of 0 or 1 on the ECOG Performance Scale
- Demonstrate adequate organ function as detailed in Section 5.1.2
- Female subject of childbearing potential should have a negative urine or serum pregnancy test within 72 hours prior to receiving retreatment with study medication.
- Female subjects of childbearing potential should be willing to use 2 methods of birth control or be surgically sterile, or abstain from heterosexual activity for the course of the study through 120 days after the last dose of study medication (Reference Section 5.7.2). Subjects of child bearing potential are those who have not been surgically sterilized or have been free from menses for > 1 year.

Note: Abstinence is acceptable if this is the usual lifestyle and preferred contraception for the subject.

- Male subjects should agree to use an adequate method of contraception starting with the first dose of study therapy through 120 days after the last dose of study therapy.

Note: Abstinence is acceptable if this is the usual lifestyle and preferred contraception for the subject.

- Does not have a history or current evidence of any condition, therapy, or laboratory abnormality that might interfere with the subject's participation for the full duration of the trial or is not in the best interest of the subject to participate, in the opinion of the treating investigator.

Subjects who restart treatment will be retreated at the same dose frequency as when they last received pembrolizumab (MK-3475). Treatment will be administered for up to one additional year.

Visit requirements are outlined in Section 6.0 – Trial Flow Chart.

### **7.1.5.3 Post-Trial**

#### **7.1.5.3.1 Safety Follow-up Visit**

The mandatory Safety Follow-Up Visit should be conducted approximately 30 days ( $\pm$  3 days) after the last dose of trial treatment or before the initiation of a new anti-cancer treatment, whichever comes first. All AEs that occur prior to the Safety Follow-Up Visit should be recorded. Subjects with an AE of Grade  $>$  1 will be followed until the resolution of the AE to Grade 0-1 or until the beginning of a new anti-cancer therapy, whichever occurs first. SAEs and ECIs that occur within 90 days of the end of treatment or before initiation of a new anti-cancer treatment should also be followed and recorded.

Subjects who are eligible for retreatment with pembrolizumab (MK-3475) (as described in Section 7.1.5.2.1) may have up to two safety follow-up visits, one after the Treatment Period and one after the Second Course Phase.

#### **7.1.5.3.2 Follow-up Visits**

Subjects who discontinue trial treatment for a reason other than disease progression will move into the Follow-Up Phase and should be assessed every 6 weeks ( $42 \pm 7$  days) by radiologic imaging to monitor disease status. After 1 year, the imaging time point will occur every 12 weeks ( $84 \pm 7$  days). Every effort should be made to collect information regarding disease status until the start of new anti-cancer therapy, disease progression determined by the investigator/site radiologist, death, end of study, or if the subject begins retreatment with pembrolizumab (MK-3475) as detailed in Section 7.1.5.2.1. Information regarding post-study anti-cancer treatment will be collected if new treatment is initiated.

Subjects who are eligible to receive retreatment with pembrolizumab (MK-3475) according to the criteria in Section 7.1.5.2.1 will move from the Follow-up Phase to the Second Course Phase when they experience disease progression. Details are provided in Section 6.2 – Trial Flow Chart for Retreatment with pembrolizumab (MK-3475).

#### **7.1.5.3.3 Survival Follow-up**

Once a subject stops receiving trial treatment, they will be followed for survival. Initially these data will be collected at the Safety Follow-up visit and 3-month Follow-up visits, and any subsequent visits for imaging that may occur until PD is confirmed or starting a new anti-cancer therapy. Once the subject stops the imaging assessments for this protocol every 6 weeks or then every 12 weeks ( $84 \pm 7$  days) after 1 year (e.g. for PD or starting a new anti-cancer therapy), the subject moves into the survival follow-up phase and should be contacted by telephone every 12 weeks ( $\pm$  7 days) to assess for survival status, until death, withdrawal of consent, or end of the study, whichever occurs first. Post-study treatments and the subject's response to them will also be collected.

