### **5.2.1.2 Immune-Related Events and Dose Modification (Withhold, Treat, Discontinue)**

#### **Dose Modification and Toxicity Management for Immune-related AEs Associated with Pembrolizumab**

AEs associated with pembrolizumab exposure may represent an immune-related response. These irAEs may occur shortly after the first dose or several months after the last dose of pembrolizumab treatment and may affect more than one body system simultaneously. Therefore, early recognition and initiation of treatment is critical to reduce complications. Based on existing clinical study data, most irAEs were reversible and could be managed with interruptions of pembrolizumab, administration of corticosteroids and/or other supportive care. For suspected irAEs, ensure adequate evaluation to confirm etiology or exclude other causes. Additional procedures or tests such as bronchoscopy, endoscopy, skin biopsy may be included as part of the evaluation. Based on the severity of irAEs, withhold or permanently discontinue pembrolizumab and administer corticosteroids.

Dose Modification and Toxicity Management Guidelines for irAEs associated with pembrolizumab monotherapy, coformulations, or IO combinations are provided in [Table 3](#).

**Table 3 Dose Modification and Toxicity Management Guidelines for Immune-related Adverse Events Associated with Pembrolizumab Monotherapy, Coformulations or IO Combinations**

General instructions:
 
 
1. Severe and life-threatening irAEs should be treated with IV corticosteroids followed by oral steroids. Other immunosuppressive treatment should begin if the irAEs are not controlled by corticosteroids.
 
2. Pembrolizumab monotherapy, coformulations or IO combinations must be permanently discontinued if the irAE does not resolve or the corticosteroid dose is not <math>\leq 10</math> mg/day within 12 weeks of the last treatment.
 
3. The corticosteroid taper should begin when the irAE is <math>\leq</math> Grade 1 and continue at least 4 weeks.
 
4. If pembrolizumab monotherapy, coformulations or IO combinations have been withheld, treatment may resume after the irAE decreased to <math>\leq</math> Grade 1 after corticosteroid taper.
 
				
irAEs	Toxicity Grade (CTCAEv4.0)	Action With Pembrolizumab Monotherapy, Coformulations or IO Combinations	Corticosteroid and/or Other Therapies	Monitoring and Follow-up

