- b. In subjects who discontinue study therapy without documented disease progression, every effort should be made to continue monitoring their disease status by radiologic imaging every 6 weeks ( $42 \pm 7$  days) in the first year and every 12 weeks ( $84 \pm 7$  days) after year 1 until (1) the start of new anti-cancer treatment, (2) disease progression as assessed by the investigator/site radiologist, (3) death, or (4) the end of the study, whichever occurs first.
- c. After documented local site assessed disease progression, or the start of new anticancer treatment; contacts are approximately every 12 weeks by telephone. Updated survival status may be requested by the Sponsor at any time during the course of the study. Upon Sponsor notification, all participants who do not/will not have a scheduled study visit or study contact during the Sponsor defined time period will be contacted for their survival status (excluding participants that have a death event previously recorded).
- d. In general, the window for each visit is  $\pm 3$  days unless otherwise noted. Study personnel will access IVRS/IWRS to obtain randomization number and study drug assignment. Cycle 1 treatment must be given within 3 days of randomization number assignment in IVRS/IWRS.
- e. Written informed consent must be obtained prior to performing any protocol specified procedure. Please note there is no specific study window for acquiring the “newly obtained” tissue specimen and it may be obtained any time before the first dose of study drug, as long as the subject has not received any intervening systemic therapy from the time the tissue was collected until the time the subject enters the study. Written consent should be obtained prior to acquiring the biopsy specimen for the study. Results of a test performed prior to the subject signing consent as part of routine clinical management are acceptable in lieu of a screening test if performed within the window specified for screening procedures (e.g., within 28 days for tumor imaging assessments or within 10 days the first dose of trial treatment for required lab tests). Screening number will be assigned when the study informed consent is signed.
- f. Signing the informed consent for future biomedical research (FBR) sample is optional. Detailed instructions for the collection and management of specimens for FBR are provided in the Procedures Manual and Section 12.2.

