- g. Prior medications – Record all medications taken within 30 days of Cycle 1. Concomitant medications – Enter new medications started during the trial through the Safety Follow-up visit. Record all medications taken for SAEs as defined in Section 7.2.
- h. AEs and laboratory safety measurements will be graded per NCI CTCAE version 4.0. All AEs, whether gradable by CTCAE or not, will also be evaluated for seriousness.
- i. Record all AEs occurring within 30 days after the last dose of trial treatment. Report all SAEs (related and unrelated to trial treatment) and ECIs occurring up until 90 days after the last dose of trial treatment or the start of new anti-cancer treatment, whichever comes first. Afterwards, report only SAEs and ECIs that are related to trial treatment.
- j. Full PE at screening visit; Direct PE for all other visits.
- k. Vital signs to include temperature, pulse, respiratory rate, weight and blood pressure. Height will be measured at screening visit only. Vital signs will be collected at screening, prior to the administration of each dose of trial treatment at every cycle, at treatment discontinuation, and at follow-up.
- l. ECOG performance status at screening to be performed within 10 days prior to Day 1 of Cycle 1. ECOG performance status will also be performed prior to the administration of each dose of trial treatment at every cycle, at treatment discontinuation, and at follow-up.
- m. For women of reproductive potential, a urine pregnancy test should be performed within 72 hours prior to first dose of trial treatment. If urine pregnancy results cannot be confirmed as negative, a serum pregnancy test performed by the local study site laboratory will be required. Pregnancy tests (serum and/or urine tests) should be repeated if required by local guidelines.
- n. Coagulation factors (PT/INR and aPTT) should be tested as part of the screening procedures for all subjects. Any subject receiving anticoagulant therapy should have coagulation factors monitored closely throughout the trial.
- o. Laboratory tests for screening are to be performed within 10 days prior to Day 1 of Cycle 1. See Section 7.1.3 for details regarding laboratory tests.

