- p. After Cycle 1, predose lab samples can be collected up to 72 hours prior to the scheduled time point. Thyroid function tests (T3, FT4 and TSH) and urinalysis should be repeated every 2 cycles after Cycle 6 up to one year of treatment. CBC and Chemistry tests should be collected predose on Day 1 of every 3 week cycle after Cycle 6. For subjects with a baseline estimated creatinine clearance below the normal institutional laboratory range, a baseline measured creatinine clearance should be performed. See Section 7.1.3 for details regarding laboratory tests. A persistent elevated alkaline phosphatase should prompt consideration for the presence of bony metastatic disease.
- q. Unresolved abnormal labs that are drug-related AEs should be followed until resolution. Labs do not need to be repeated after the end of treatment if labs are within normal range.
- r. Blood for serum and blood for plasma correlative studies is to be collected only predose at Cycle 1. See Procedures Manual. Any leftover samples from the correlative blood studies will be stored for future biomedical research if the subject signs the FBR consent
- s. Whole blood sample for RNA/DNA correlative studies should be collected predose at Cycles 1, 2, and 3, and again at treatment discontinuation.. See Procedures Manual. Any leftover samples from the correlative blood studies will be stored for future biomedical research if the subject signs the FBR consent.
- t. This sample should be drawn for planned genetic analysis of DNA and drug response unless there is either a documented law or regulation prohibiting collection, or unless the IRB/IEC does not approve of the collection of the sample for these purposes. If the sample is collected, any leftover extracted DNA will be stored for future biomedical research if the subject signs the FBR consent.

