## **7.2.3 Immediate Reporting of Adverse Events to the Sponsor**

### **7.2.3.1 Serious Adverse Events**

A serious adverse event is any adverse event occurring at any dose or during any use of Sponsor's product that:

- Results in death;
- Is life threatening;
- Results in persistent or significant disability/incapacity;
- Results in or prolongs an existing inpatient hospitalization;
- Is a congenital anomaly/birth defect;
- Is an other important medical event

**Note:** In addition to the above criteria, adverse events meeting either of the below criteria, although not serious per ICH definition, are reportable to the Sponsor in the same timeframe as SAEs to meet certain local requirements. Therefore, these events are considered serious by the Sponsor for collection purposes.

- Is a new cancer (that is not a condition of the study);
- Is associated with an overdose;

Refer to [Table 7](#) for additional details regarding each of the above criteria.

For the time period beginning when the consent form is signed until treatment allocation/randomization, any serious adverse event, or follow up to a serious adverse event, including death due to any cause other than progression of the cancer under study (reference Section 7.2.3.3 for additional details), that occurs to any subject must be reported within 24 hours to the Sponsor if it causes the subject to be excluded from the trial, or is the result of a protocol-specified intervention, including but not limited to washout or discontinuation of usual therapy, diet, placebo treatment or a procedure.

For the time period beginning at treatment allocation/randomization through 90 days following cessation of treatment, or 30 days following cessation of treatment if the subject initiates new anticancer therapy, whichever is earlier, any serious adverse event, or follow up to a serious adverse event, including death due to any cause other than progression of the cancer under study (reference Section 7.2.3.3 for additional details), whether or not related to the Sponsor's product, must be reported within 24 hours to the Sponsor either by electronic media or paper. Electronic reporting procedures can be found in the EDC data entry

guidelines. Paper reporting procedures can be found in the Investigator Trial File Binder (or equivalent)

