### **7.2.3.2 Events of Clinical Interest**

Selected non-serious and serious adverse events are also known as Events of Clinical Interest (ECI) and must be reported to the Sponsor.

For the time period beginning when the consent form is signed until treatment allocation/randomization, any ECI, or follow up to an ECI, that occurs to any subject must be reported within 24 hours to the Sponsor if it causes the subject to be excluded from the trial, or is the result of a protocol-specified intervention, including but not limited to washout or discontinuation of usual therapy, diet, placebo treatment or a procedure.

For the time period beginning at treatment allocation/randomization through 90 days following cessation of treatment, or 30 days following cessation of treatment if the subject initiates new anticancer therapy, whichever is earlier, any ECI, or follow up to an ECI, whether or not related to the Sponsor's product, must be reported within 24 hours to the Sponsor, either by electronic media or paper. Electronic reporting procedures can be found in the EDC data entry guidelines. Paper reporting procedures can be found in the Investigator Trial File Binder (or equivalent).

Events of clinical interest for this trial include:

1. an overdose of Sponsor's product, as defined in Section 7.2.1 - Definition of an Overdose for This Protocol and Reporting of Overdose to the Sponsor, that is not associated with clinical symptoms or abnormal laboratory results.
2. an elevated AST or ALT lab value that is greater than or equal to 3X the upper limit of normal and an elevated total bilirubin lab value that is greater than or equal to 2X the upper limit of normal and, at the same time, an alkaline phosphatase lab value that is less than 2X the upper limit of normal, as determined by way of protocol-specified laboratory testing or unscheduled laboratory testing.\*

\*Note: These criteria are based upon available regulatory guidance documents. The purpose of the criteria is to specify a threshold of abnormal hepatic tests that may require an additional evaluation for an underlying etiology. The trial site guidance for assessment and follow up of these criteria can be found in the Investigator Trial File Binder (or equivalent).

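### Subjects who stop for progression and start no new therapy have no scheduled adverse-event review after the 30-day visit, although SAEs and ECIs are reportable to day 90

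*Combined protocol and SAP*

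**What the plan says.** **The reporting window.** Section 7.2.3.1 requires SAEs to be reported, whether or not related, "through 90 days following cessation of treatment, or 30 days following cessation of treatment if the subject initiates new anticancer therapy, whichever is earlier". Section 7.2.3.2 sets the same limits for ECIs. Footnote i of the flow chart in 6.1 tells sites: "Report all SAEs (related and unrelated to trial treatment) and ECIs occurring up until 90 days after the last dose of trial treatment". After the window, only related SAEs and ECIs are reportable.

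**The reason for a long window.** Section 5.2.1.2 states: "These irAEs may occur shortly after the first dose or several months after the last dose of pembrolizumab treatment".

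**The contacts after treatment.**
- Section 7.1.5.3.1: one mandatory safety visit at 30 ± 3 days after the last dose.
- Section 7.1.5.3.2 and footnote b: Follow-up Visits only for subjects who stop for a reason other than progression, every 6 weeks in the first year and every 12 weeks later.
- Section 7.1.5.3.3: once imaging stops, for example for progression or new therapy, "the subject moves into the survival follow-up phase and should be contacted by telephone every 12 weeks". The stated purpose is survival status; post-study treatments and the response to them are also collected.
- Footnote c of 6.1: "After documented local site assessed disease progression, or the start of new anticancer treatment; contacts are approximately every 12 weeks by telephone".

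**The flow charts.** In 6.1 and 6.2 the adverse-event review row is marked under Safety Follow-up and under Follow Up Visits. It has no mark under Survival Follow-up.

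**The concern.** A reporting duty finds events only if someone asks or an event reaches the site by another route. For subjects who stop without progression, the charts schedule that question at Follow-up Visits. For those who stop for progression, nothing scheduled asks it after about day 30. How well late SAEs and ECIs are found then depends on why the subject stopped treatment.

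This matters because the protocol itself expects late immune-related events, and because Section 8.2.3.2 names SAEs and ECIs as safety measures. Section 7.2.3.3 adds a further reason. Disease progression is exempt from SAE reporting, but events that prove not to be progression must be forwarded as SAEs. If nobody asks about adverse events after progression, a late immune-related hospitalization or death may more easily be put down to the cancer.

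**Working it through.** The plan states no figure to reproduce. The check sets the schedule against the window, in days from last dose unless noted.

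**1. Time without a scheduled adverse-event review (stopped for progression, no new therapy)**
- Safety visit: 30 ± 3 = days 27 to 33.
- Window closes: day 90.
- Uncovered time: 90 − 33 = 57 days to 90 − 27 = 63 days; nominally 90 − 30 = 60 days.
- Share of the window: 60/90 = 67%.

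**2. Position of the first telephone call**
- The interval is 12 weeks ± 7 days, or 84 ± 7. The documents do not say what it is counted from.
- Counted from last dose: days 77 to 91, so mostly before the window closes.
- Counted from the 30-day visit: 27 + 77 = 104 to 33 + 91 = 124, after the window has closed.
- In either case no adverse-event question is scheduled for the call.

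**3. Comparison group (stopped without progression)**
- First year: visits at 42 ± 7 = days 35 to 49 and 84 ± 7 = days 77 to 91 after discontinuation.
- Assume discontinuation is recorded 0 to 21 days after the last dose. The first visit then falls on days 35 to 49 + 21 = 70, always inside the window. The second falls on days 77 to 91 + 21 = 112, inside it or not.
- Result: one or two adverse-event reviews after the 30-day visit and before day 90.
- After the first year: the first visit is the 84 ± 7 one, so none or one review before day 90. The timing is then close to that of the telephone call, but the visit carries an adverse-event review and the call does not.

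**4. Other text that might fill the space**
- Section 7.1.5.3.1 says SAEs and ECIs within 90 days should be followed and recorded, but schedules no contact to find them.
- Section 7.2.3.1 keeps related SAEs reportable beyond the window when they come to the investigator's attention. That is passive.
- Section 7.2.3.2 ties ECI assessment to each dose, so it ends with treatment.
- Section 7.1.5.3.3 mentions 3-month follow-up visits. Neither chart contains one, and no adverse-event review is attached to them.
- Adverse events above Grade 1 are followed to Grade 0–1 or new therapy (7.1.5.3.1), and unresolved drug-related laboratory abnormalities are followed (footnote q). Both rules cover events already present, not new ones.

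**5. Where the window ends if new therapy starts on day t**
- 7.2.3.1 and the general rule in 7.2.3.2: day 30 after treatment.
- Footnote i in 6.1 and 6.2: "up until 90 days after the last dose of trial treatment or the start of new anti-cancer treatment, whichever comes first", so day t or day 90, whichever is earlier. Section 7.1.5.3.1 also refers to the start of new therapy.
- 7.2.3.2, item 3: day t + 30 or day 90, whichever is earlier.

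These three rules give different closing days for the same subject.

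**The case against.** The strongest reply is that a reporting window longer than the visit schedule is a design choice and not a contradiction. The 24-hour duty to report SAEs and ECIs applies to every subject regardless of relatedness, and related SAEs have no time limit. Section 7.1.2.1 allows more frequent assessment where clinically indicated. Subjects who stop for toxicity do attend Follow-up Visits. New anticancer therapy shortens the window for some progressors. Section 7.1.5.3.3 gives the purpose of the call without forbidding other questions. A separate ECI guidance document, which is not among these documents, might cover surveillance after treatment.

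Most of this stands as mitigation. None of it schedules an enquiry in the group concerned, and sites work from the charts.

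The objection fully succeeds against three stronger readings that a reader might infer.
- *The laboratory waiver widens the difference between the groups.* Footnote q says: "Labs do not need to be repeated after the end of treatment if labs are within normal range". It applies to all subjects, and no laboratory tests are marked at Follow-up Visits. It does not separate the groups, and drawing a panel at day 30 could not detect an event arising on days 31 to 90.
- *The planned confidence intervals for immune-related events of Grade 2 or higher and for Grade 3–5 events both rest on under-counted data.* Non-serious events that are not ECIs are collected only to day 30 in everyone, and Section 8.2.5.2 states no collection window for either interval. Only late SAEs and ECIs could be affected.
- *A number of missed events can be given.* It would need the share stopping for progression, the share of those starting no new therapy, the event risk on days 31 to 90 and the passive capture rate. The documents give none of these.

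**Conclusion.** The point holds for new-onset SAEs and ECIs on about days 31 to 90 in subjects who stopped for progression and started no new therapy. They have no scheduled adverse-event review for 57 to 63 days of a 90-day window. Subjects without progression have one or two such reviews in that time in the first year, and none or one later, with discontinuation assumed to be recorded within 21 days of the last dose.

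The consequence is limited. It concerns late SAEs and ECIs and any summary that includes them, in a study where safety is a secondary objective. The response-rate analysis is unaffected. The direction is towards under-counting, but the size cannot be derived from the documents. The conclusion assumes that the unseen ECI guidance adds no scheduled contact after treatment. The change is worth making because it is specific and nearly free and alters what is captured; the point does not call the trial's main conclusions into question.

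**What to change.** 1. In 6.1 and 6.2, mark SAE/ECI review at the first Survival Follow-up contact for subjects not attending Follow-up Visits.
2. Anchor that contact at or just after day 90 from the last dose, for example days 90 to 97, so that one enquiry covers the whole window.
3. Add the SAE/ECI question to the content of the call in 7.1.5.3.3.
4. In the same edit, reconcile the new-therapy cut-offs in footnote i of both charts, 7.1.5.3.1, 7.2.3.1 and 7.2.3.2 (general rule and item 3), so that the window has one closing rule. Either chart the 3-month follow-up visits in 7.1.5.3.3 or remove the mention.

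The cost is a wording and flow-chart change, one added question and a slightly re-timed call that is already planned. No treatment rule or laboratory requirement changes. The reported rate of late events may rise slightly. For subjects whose window has already closed the change cannot help, and the study report should state that late SAEs and ECIs were captured passively after progression.
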